For Aim 1, we will enroll two groups: 15 participants with good sleep quality (sleep efficiency by actigraphy $\geq 85\%$) and 15 participants with poor sleep quality (sleep efficiency by actigraphy $< 85\%$). All participants in Aim 1 will receive a placebo generated by the investigational pharmacy at Barnes-Jewish Hospital. For Aim 2, an additional 30 participants with poor sleep quality (sleep efficiency by actigraphy $< 85\%$) will be recruited and will receive either suvorexant 10 mg or suvorexant 20 mg, a dual orexin receptor antagonist approved by the Food and Drug Administration (FDA) for the treatment of insomnia (approved doses 5-20 mg). This group will be compared to the 15 participants with poor sleep quality in Aim 1 who received placebo. Participants who have poor sleep efficiency will be randomized to either placebo or suvorexant. There will be a total of 60 participants who complete the study.

Sampling plan and justification:

- Power calculations in the “Statistical Analysis and Power Calculation” portion of the research plan were based on preliminary data about the area under the curve differences in A β during a 10-hour sleep period (23:00-09:00) in participants with different sleep efficiency. Due to concerns about recruitment if participants have to repeat the study, the study power calculation is based on each participant completing the study once without repeating. 15 participants are required for each study arm (total N=60).
- Children will be excluded and age range will be limited to 45-65, as detailed in the previous section “Subject population characteristics”.

Vulnerable populations: We will not enroll participants from vulnerable populations.

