Protections for research involving vulnerable populations: This project does not involve vulnerable populations.

Plan for adverse events: Response to an adverse event or risk will differ based on the type and severity of the event. A Data Safety Monitoring Committee (DSMC) will serve to mitigate these risks and ensure a formal process for dealing with adverse events.

- *Data Safety Monitoring Committee:* A DSMC consisting of experts in the study procedures and the effects of sleep disorders on cardiac and psychiatric morbidities has been established for the proposed study.
 - Qualified individuals monitoring the study: The DSMC members have substantial experience and expertise in this area of research and in clinical research, and are qualified to monitor the study.
 - The DSMC will meet prior to enrollment of any participants, to review study procedures and potential adverse events, and then provide guidance on HRPO application and consent/informational materials.
- *Web-Based Instruction on Conducting Human Research:* In accordance with the NIH policy effective October 1, 2000, this is to certify that Washington University key personnel involved in the design and conduct of the human subjects research aspect of this proposal have been educated on the protection of human research participants. An interactive web-based program that provides information on conducting human research and the informed consent process is organized into five modules. These modules include detailed information, examples and exercises related to basic principles, history, consent form process, and after approval requirements such as continuing review and adverse events.
- *Review of adverse events:* All personnel who will be in contact with participants and/or data are prepared to identify adverse events and have been instructed to report their occurrence immediately to the principal investigator.
- *Definition:* An adverse event will be defined as any negative change in health related to study-related procedures.
- *Classification of Events:* A Safety Documentation form will assess for details of any adverse events, severity, and relatedness to study procedures.
- *Data Collection Procedures for Adverse Events:* At each visit and with each interaction/phone call, adverse events will be screened for and recorded. If any adverse events have occurred, these will be logged in the Safety Documentation form.

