- *Reporting Procedures:* The Safety Documentation form will be discussed during the DSMC meetings. The DSMC will meet according to participant completion goals (after 15, 23, 30, 38, and 45 participants complete the study). If a serious adverse event occurs, the DSMC will meet as soon as possible to determine the course of action. If the DSMC deems changes to the study are necessary for safety reasons, the study will halt immediately until the changes have been approved through the Washington University HRPO.

- *Criteria for stopping the study:* Circumstances that would warrant stopping the study are not anticipated. However, should any circumstances arise that compromise the safety of the participants, they will be reported to the DSMC who will suspend research until appropriate safeguards allow continuation of the study.
- *Adverse Event Reporting Period:* There will not be a set end-date for reporting adverse events.
 - Expected adverse events (*i.e.* are listed above and on consent forms) will be discussed at DSMC meetings. Also, they will be reported to the HRPO during annual renewals.
 - Unexpected serious adverse events will be reported within 10 days, per HRPO requirements.

The only anticipated adverse events that would require medical intervention are:

1. A post-lumbar catheter headache that does not resolve with conservative measures such as rest, hydration, and caffeine intake. This will be treated with “blood patch” in the Clinical Research Unit, at no cost to the participant.
2. Side effects to suvorexant such as somnolence and confusion upon waking. Risks from suvorexant are minimized with the inclusion/exclusion criteria and that participants will only receive the drug for 2 nights in the monitored setting of the Clinical Research Unit at Washington University. If any severe adverse events occur on suvorexant, then the drug will be discontinued and the participant monitored closely.

3. Potential Benefits of the Proposed Research to Human Subjects and Others

Potential benefits to participants

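### Scheduled DSMC meetings stop at 45 completers although 60 are planned, so the last 15 (25%) have no scheduled DSMC review of their safety forms and expected or non-serious events

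*Combined protocol and SAP*

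**What the plan says.** The committee's schedule is in section 2.B, Protections Against Risk, under Reporting Procedures: "The DSMC will meet according to participant completion goals (after 15, 23, 30, 38, and 45 participants complete the study". The Plan for adverse events in the same section adds one meeting before any enrolment. No other routine meeting is listed.

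The planned size is in section 1.A: "There will be a total of 60 participants who complete the study". Statistical Analysis and Power Calculation gives the same total as four groups of 15.

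These meetings are where routine safety data are considered. Reporting Procedures states: "The Safety Documentation form will be discussed during the DSMC meetings". Under Adverse Event Reporting Period, expected events (those that "are listed above and on consent forms) will be discussed at DSMC meetings") take the same route, with a second route to the ethics office: "Also, they will be reported to the HRPO during annual renewals".

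Three provisions do not depend on the schedule:

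- Serious events: "If a serious adverse event occurs, the DSMC will meet as soon as possible to determine the course of action".
- Circumstances that compromise participant safety: "they will be reported to the DSMC who will suspend research until appropriate safeguards allow continuation of the study".
- Staff in contact with participants or data, for any adverse event: they "have been instructed to report their occurrence immediately to the principal investigator".

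Section 5 also assigns monitors to follow adverse events with no stated end. It requires suspension if an adverse event raises the risk to participants, and it sends yearly summaries to the HRPO.

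**The concern.** The committee's calendar ends 15 completers short of the planned sample. Up to 45 completers, safety forms and expected events come before the committee every 7 or 8 completers after the first 15. After that, nothing routine is scheduled.

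Every participant has a lumbar catheter for 36 hours, and the commonest harms, catheter headache and blood patch, are expected events. A rise in these among the last 15 need not involve a serious event. It would reach the DSMC only if someone first judged that safety was compromised. Pooled review exists to show a pattern that single reports may not, and after 45 completers the committee has no scheduled point at which to see one and act on it.

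**Working it through.** **Planned total.** Four groups of 15 (good sleepers on placebo; poor sleepers on placebo, suvorexant 10 mg and suvorexant 20 mg): 15 + 15 + 15 + 15 = 60. This reproduces the figure in section 1.A.

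**Uncovered completers.** Last scheduled meeting: 45. 60 − 45 = 15, and 15/60 = 25%.

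**Schedule against both totals.**

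| Meeting after | % of 60 | % of 45 |
|---|---|---|
| 15 | 25 | 33 |
| 23 | 38 | 51 |
| 30 | 50 | 67 |
| 38 | 63 | 84 |
| 45 | 75 | 100 |

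**Spacing.** The listed points equal 7.5 × k rounded up for k = 2 to 6: 15, 22.5→23, 30, 37.5→38, 45. The protocol does not state this rule; it is inferred. Continuing it gives 7.5 × 7 = 52.5→53 and 7.5 × 8 = 60.

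**Expected events in the uncovered group.** Section 1.C (Lumbar Catheter) gives headache in 50–80% of participants and a persistent headache needing a blood patch in 30% or less. The text does not make clear whether the 30% is a share of those with headache or of all participants, so both are shown.

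| | Last 15 | The 8 between 45 and 53 |
|---|---|---|
| Headaches, n × 0.5 to n × 0.8 | 7.5 to 12 | 4.0 to 6.4 |
| Blood patches at most, share of those with headache (n × 0.5 × 0.3 to n × 0.8 × 0.3) | 2.25 to 3.6 | 1.2 to 1.92 |
| Blood patches at most, share of all (n × 0.3) | 4.5 | 2.4 |

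**What each added meeting could do.** A meeting after 53 brings in 53 − 45 = 8 further completers while up to 60 − 53 = 7 have still to complete. A meeting after 60 cannot alter any admission.

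**The case against.** The quotations and the subtraction are not in dispute. The case on the other side has four parts.

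*The count may refer to the randomised participants.* The schedule reaches exactly 100% at 45, which is the number of randomised poor sleepers. It may count only them, or be left over from a 45-person design, in which case this is an inconsistency to clarify. That is plausible, but the text sets no such limit, and section 1.A uses almost the same phrase for all 60. On the randomised-only reading, the 15 good sleepers, who have the same catheter, would not count toward any meeting. The uncovered number would then depend on when they finish and could be below 15. The sentence would still need correcting.

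*Other safeguards continue.* This is true, and it limits the harm. The section 5 suspension rule is not confined to serious events, and the section 5 monitors may be the DSMC members themselves; their names are removed, so this cannot be settled. But the suspension rule needs a prior judgement that risk has risen, the monitors have no stated meeting schedule, and HRPO reports are annual. None of these is a scheduled DSMC review.

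*Eight more people can show little.* At an 80% headache rate, all 8 having a headache has probability 0.8^8 = 0.17. At a 30% blood-patch rate, 5 or more of 8 has probability 0.058. This stands as a limit on what the 8 show alone: only a marked excess would stand out. However, the committee would look at the cumulative data on 53 and at the individual forms, and could still change conduct for up to 7 participants.

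*The fix is partly preference.* No rule requires steps of 7.5, and the meeting after 60 changes no one's care. That is accepted, and it is why one added meeting is the minimum.

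**Conclusion.** The concern holds, as a minor one. Followed as written, the plan gives 15 of 60 completers (25%) no scheduled DSMC review of their safety forms and expected or non-serious events. This assumes that the meeting triggers count all participants, as the wording implies, and that 60 complete as planned. If the interim analysis mentioned under Alternative Approaches led to more participants, the uncovered share would exceed 25%.

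The gap is confined to the committee's routine pooled review. Immediate serious-event oversight is intact, and the documents show no harm to any participant. The event counts rest on the protocol's own rates and indicate how much routine safety information would go without scheduled review. They do not show that a rise would occur, or that it would be detected.

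**What to change.** In section 2.B, Reporting Procedures, extend the list of meeting points to 15, 23, 30, 38, 45, 53 and 60 completers, and state that the count covers all participants, good sleepers included. The meeting after 53 is the one that can still change conduct; the one after 60 closes out the remaining safety forms. If only one can be added, add the one after 53.

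The cost is two more meetings of an existing committee (one at minimum) and an edit to one sentence, submitted as an amendment. Sample size, procedures and analysis do not change.
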